10.5.2 Safety Analysis Populations

The All Participants as Treated (APaT) population will be used for the analysis of safety data in this study. The APaT population consists of all participants who received at least 1 dose of study vaccination and had clinical follow-up for safety.

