Study Stage	Base Stage (Participants 9-26 years of age)						Extension Stage (Participants 9-19 years of age)					Notes
	Visit 1 Day 1 Vaccination 1	Visit 2 Month 1	Visit 3 Month 2 Vaccination 2	Visit 4 Month 3	Visit 5 Month 6 Vaccination 3	Visit 6 Month 7	Visit 7 Month 12	Visit 8 Month 24	Visit 9 Month 36	Visit 10 Month 48	Visit 11 Month 60	
Study Visit Number/ Title												
Scheduled Day	1	32	62	93	184	215	366	732	1097	1462	1827	
Scheduling Window:	± 0 days	31 to 38 days after Vaccination 1	± 21 days	31 to 52 days after Vaccination 2	± 28 days	31 to 49 days after Vaccination 3	± 28 days	± 28 days	± 28 days	± 28 days	± 28 days	
Assign Treatment/ Randomization Number	X											
Study Vaccine Administration	X		X		X							The interval between the date of consent and the date of the Day 1 visit should be no more than 14 days apart. If the interval is 15 days or longer, then the participant must be re-consented. All the study-related procedures for Day 1 visit except informed consent/assent, baseline number assignment, participant identification card, should be performed on the same day of Day 1 vaccination.
Efficacy procedures												
Serum for Anti-HPV Antibody Testing	X					X	X	X	X	X	X	The serum collected at Day 1 for anti-HPV measurements must be collected before vaccination.

Study Stage	Base Stage (Participants 9-26 years of age)						Extension Stage (Participants 9-19 years of age)					Notes
	Visit 1 Day 1 Vaccination 1	Visit 2 Month 1	Visit 3 Month 2 Vaccination 2	Visit 4 Month 3	Visit 5 Month 6 Vaccination 3	Visit 6 Month 7	Visit 7 Month 12	Visit 8 Month 24	Visit 9 Month 36	Visit 10 Month 48	Visit 11 Month 60	
Study Visit Number/ Title												
Scheduled Day	1	32	62	93	184	215	366	732	1097	1462	1827	
Scheduling Window:	± 0 days	31 to 38 days after Vaccination 1	± 21 days	31 to 52 days after Vaccination 2	± 28 days	31 to 49 days after Vaccination 3	± 28 days	± 28 days	± 28 days	± 28 days	± 28 days	
Safety procedures												
30-minute Post-Vaccination Observation Period	X		X		X							
Provide Vaccination Report Card (VRC) to Participant	X		X		X							
Review and Collect VRC data		X		X		X						Phone call contacts are to be conducted every week for each participant by study site personnel before the VRCs are returned. The main purpose of phone call visit is to remind the participant to record the VRC and answer any questions related to VRC from participants.
Clinical Follow-up for Safety	X	X	X	X	X	X	X	X	X	X	X	

3 Introduction

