6.1.2 Inclusion Criteria for Extension Stage

1. Participant was enrolled in the 9-19 years old group in the base stage.
2. Participant has received 3 doses of V501 during the base stage.
3. Participant and participant's legally acceptable representative (if applicable) provides written informed consent/assent for Study Extension.

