6.2 Exclusion Criteria

Participants are excluded from the study if any of the following criteria apply:

The following exclusion criteria are only applicable for the base stage.

Participants enrolled in the 20-26 years old group will not participate in the extension stage, and participants enrolled in the 9-19 years old group who reported overdose or received non-study HPV vaccine during the base stage will be excluded from the extension stage.

Medical Conditions[†]

1. Participant has a fever (defined as axillary temperature $\geq 37.1^{\circ}\text{C}$) within 24 hours prior to the Day 1 vaccination (if the participant meets this exclusion criterion, the Day 1 visit may be rescheduled for a time when this criterion is not met).
2. Participant has a history of severe allergic reaction (e.g. swelling of the mouth and throat, difficulty breathing, hypotension, or shock) that required medical intervention.
3. Participant is allergic to any vaccine component, including aluminum, yeast, or BENZONASETM (nuclease, Nycomed [used to remove residual nucleic acids from this and other vaccines]).
4. Participant with known thrombocytopenia or any coagulation disorder that would contraindicate intramuscular injections.
5. Participant is currently immunocompromised or has been diagnosed as having congenital or acquired immunodeficiency, human immunodeficiency virus (HIV) infection, lymphoma, leukemia, systemic lupus erythematosus (SLE), rheumatoid arthritis, juvenile rheumatoid arthritis (JRA), inflammatory bowel disease, or other autoimmune condition.
6. Participant has a history of splenectomy.
7. Participant has any condition which in the opinion of the investigator might interfere with the evaluation of the study objectives.
8. Participant has a history of recent or ongoing alcohol or other drug abuse. Alcohol abusers are defined as those who drink despite recurrent social, interpersonal, and legal problems as a result of alcohol use.
9. Participant has a history of a positive test for HPV.
10. Participant has any history of abnormal Pap test showing squamous intraepithelial lesion (SIL) or ASC-US, ASC-H, or biopsy showing cervical intraepithelial neoplasia (CIN), adenocarcinoma in situ or cervical cancer.
11. Participant has a history of external genital wart, vulvar intraepithelial neoplasia (VIN), vaginal intraepithelial neoplasia (VaIN), vulvar cancer or vaginal cancer.

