Investigators are not obligated to actively seek AE or SAE or other reportable safety events in former study participants. However, if the investigator learns of any SAE, including a death, at any time after a participant has been discharged from the study, and he/she considers the event to be reasonably related to the study treatment or study participation, the investigator must promptly notify the sponsor.

All initial and follow-up AEs, SAEs and other reportable safety events will be recorded and reported to the sponsor or designee within the timeframes as indicated in [Table 2](#).

Table 2 Reporting Time Periods and Timeframes for Adverse Events and Other Reportable Safety Events

Type of Event	Reporting Time Period: Consent to Randomization/Allocation	Reporting Time Period: Randomization/Allocation through Protocol-Specified Follow-up Period	Reporting Time Period: After the Protocol Specified Follow-up Period	Timeframe to Report Event and Follow-up Information to SPONSOR:
Non-Serious Adverse Event (NSAE)	Report if: - due to protocol-specified intervention - causes exclusion - participant is receiving placebo run-in or other run-in treatment	Report all	Not required	Per data entry guidelines
Serious Adverse Event (SAE)	Report if: - due to protocol-specified intervention - causes exclusion - participant is receiving placebo run-in or other run-in treatment	Report all	Report all	Within 24 hours of learning of event
Pregnancy/ Lactation Exposure	Report if: - due to intervention - causes exclusion	Report all	Report all	Within 24 hours of learning of event
Cancer	Report if: - due to intervention - causes exclusion	Report all	Report all	Within 5 calendar days of learning of event
Overdose	Report if: - receiving placebo run-in or other run-in medication	Report all	Report all	Within 5 calendar days of learning of event

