10.1 Statistical Analysis Plan Summary

Key elements of the statistical analysis plan are summarized below; the comprehensive plan is provided in Sections 10.2-10.12.

Study Design Overview	A Phase 3 Open-Label Clinical Trial to Study the Immunogenicity, Safety and Tolerability of Recombinant Human Papillomavirus Quadrivalent (Types 6, 11, 16, 18) Vaccine (V501) in Chinese Girls Aged 9-19 Years and Young Women Aged 20-26 Years.
Treatment Assignment	It is a single-arm, open-label study. All enrolled participants will receive a 3-dose regimen of V501. Stratification factors are provided in Section 7.3.1.
Analysis Populations	Immunogenicity: Per protocol immunogenicity (PPI) population Safety: All Participants as Treated (APaT) population

Primary Endpoint(s)	
Base stage:
 
The primary endpoints are cLIA GMTs to each of HPV 6, 11, 16, and 18 at 1 month post dose 3.
 
Extension stage:
 
• cLIA GMTs and seropositivity percentages to each of HPV 6, 11, 16, and 18 at Month 12, Month 24, Month 36, Month 48, and Month 60.• IgG LIA GMTs and seropositivity percentages to each of HPV 6, 11, 16, and 18 at Month 12, Month 24, Month 36, Month 48, and Month 60.
Secondary Endpoints	
Base stage:
 
The key secondary endpoints are cLIA seroconversion percentages to each of HPV 6, 11, 16, and 18 at 1 month post dose 3.
 
Extension stage:
 
Proportion of participants experiencing SAEs.

Statistical Methods for Key Immunogenicity Analyses	
Base stage:
 
The primary hypotheses (H_1) of non-inferiority of GMTs for each of HPV types 6, 11, 16, and 18 will be addressed by 4 one-sided tests of non-inferiority, with $H_0: \text{GMT}_1/\text{GMT}_2 \leq 0.67$ and $H_a: \text{GMT}_1/\text{GMT}_2 > 0.67$, at $\alpha=0.025$. GMT_1 and GMT_2 represent the GMTs at 1 month post dose 3 in girls aged 9-19 years and young women aged 20-26 years, respectively.
 
Extension stage:
 
GMTs and seropositivity percentages to the each of HPV types 6, 11, 16, 18 will be summarized and plotted.

Statistical Methods for Key Safety Analyses	All safety data will be summarized as frequencies and percentages for the two age groups in the base stage and for the 9-19 years old group in the extension stage.
Interim Analyses	No interim analysis is planned.

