[†] P=Primary approach; S=Supportive approach.

[‡] Statistical models are described in further detail below:

ANPS = all type-specific naïve participants with serology; CI = confidence interval; GMT = geometric mean titer; PPI = per-protocol immunogenicity.

PBNA results (GMTs and seroconversion percentages) will be summarized as exploratory objective. The PBNA results of the base stage may be summarized in a supplemental report after the data are available.

Extension stage:

Participants in the 9-19 years old group who have completed 3 doses of study vaccination will be followed up to Month 60 to evaluate the persistence of the serum antibody titers for each of HPV 6, 11, 16 and 18 at Month 12, Month 24, Month 36, Month 48, and Month 60. Both cLIA and IgG LIA will be used to measure GMTs and seropositivity percentages.

Table 5 summarizes the immunogenicity persistence analyses for the extension stage.

Table 5 Analysis Strategy for Immunogenicity Variables – Extension Stage

Endpoint/Variable (Description, Time Point)	Primary vs. Supportive Approach [†]	Statistical Method	Analysis Population	Missing Data Approach
cLIA GMTs to HPV 6, 11, 16 and 18 at Month 12, Month 24, Month 36, Month 48, and Month 60	P	Point and 95% CI estimation will be performed by using an ANOVA model; no statistical testing and between group 95% CI will be given.	PPI	Observed data only
cLIA % seropositivity to HPV 6, 11, 16 and 18 at Month 12, Month 24, Month 36, Month 48, and Month 60	P	Point and 95% CI estimation based on exact method; no statistical testing and between group 95% CI will be given.	PPI	Observed data only
IgG LIA GMTs to HPV 6, 11, 16 and 18 at Month 12, Month 24, Month 36, Month 48, and Month 60	P	Point and 95% CI estimation will be performed by using an ANOVA model; no statistical testing and between group 95% CI will be given.	PPI	Observed data only
IgG LIA % seropositivity to HPV 6, 11, 16 and 18 at Month 12, Month 24, Month 36, Month 48, and Month 60	P	Point and 95% CI estimation based on exact method; no statistical testing and between group 95% CI will be given.	PPI	Observed data only
cLIA GMTs to HPV 6, 11, 16 and 18 at Month 12, Month 24, Month 36, Month 48, and Month 60	S	Reverse cumulative distribution curve (RCD) at Month 12, Month 24, Month 36, Month 48, and Month 60	PPI	Observed data only

[†] P=Primary approach; S=Supportive approach.
CI = confidence interval; GMT = geometric mean titer; PPI = per-protocol immunogenicity.

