10.6.2 Statistical Methods for Safety Analyses

Base stage:

Safety and tolerability will be assessed by clinical review of all safety data collected after each study vaccination.

Summary statistics, counts and percentage without confidence interval, will be provided by age group. Proportions of participants with solicited injection-site AEs, solicited systemic AEs within 14 days following study vaccination will be given. Maximum axillary temperatures recorded on the VRC from Day 1 to Day 5 post-vaccination will be summarized.

In addition, proportions of participants with all injection-site and systemic AEs (including solicited and non-solicited AEs) within 30 days following study vaccination, and proportions of participants with SAEs through to Month 7 will also be summarized.

Both Sponsor's criteria (See "Assessment of Intensity" in Section 12.3 Appendix 3) and CFDA's criteria (See Section 12.5 Appendix 5 – Country-specific Requirements) will be applied to assess the intensity of adverse events. The incidence of greatest adverse event intensity reported by a participant based on both the two criteria will be tabulated for: all injection-site AEs and all systemic AEs within 30 days following any study vaccination.

All pregnancy outcomes and infant SAEs will be summarized.

Extension stage:

Summary statistics, including counts and proportion of participants with SAEs during the extension stage will be summarized for 9-19 years old participants.

In addition, pregnancy outcomes and infants SAEs during the extension stage will be summarized.

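### Does the extension-stage SAE proportion lack a denominator, and is it therefore biased low?

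*Combined protocol and SAP*

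**What the plan says.** Section 10.5.2 has a single safety population, All Participants as Treated (APaT), for all safety data in the study: "The APaT population consists of all participants who received at least 1 dose of study vaccination and had clinical follow-up for safety". No stage is mentioned.

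For the extension, Section 10.6.2 states that "counts and proportion of participants with SAEs during the extension stage will be summarized for 9-19 years old participants". The summary in Section 10.1 says safety data will be presented "for the 9-19 years old group in the extension stage". The SAE proportion is the extension's only secondary endpoint (Section 4), and Section 10.8 notes that the extension has no hypothesis.

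Entry is narrower than APaT membership. Section 6.1.2 requires that "Participant has received 3 doses of V501 during the base stage", together with separate consent or assent for the extension. Section 6.2 adds that girls "who reported overdose or received non-study HPV vaccine during the base stage will be excluded from the extension stage". In the schedule of activities (Section 2), the row "Clinical Follow-up for Safety" is marked at every visit from Day 1 to Month 60, and the extension columns carry the 9-19 age label.

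**The concern.** A girl who had one dose and was seen at Month 1 meets both APaT conditions. So does a girl who finished the base stage and declined the extension. If APaT is applied unaltered to the extension, both sit in the denominator of an SAE proportion covering a period in which they were not followed. Section 9.3.1 says that "Investigators are not obligated to actively seek AE or SAE or other reportable safety events in former study participants", so their SAEs would rarely be recorded. A spontaneous report remains possible, but capture is not comparable with scheduled visits. The proportion would then be too low.

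The extension immunogenicity text in Section 10.6.1 looks more careful. It says "Participants in the 9-19 years old group who have completed 3 doses of study vaccination will be followed up to Month 60", and Table 5 restricts the analysis to observed data. The safety text has neither limit. Two analysts could therefore print different proportions for a named secondary endpoint from the same sentences.

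**Working it through.** **Reproducing the plan's safety figures (Section 10.9.2).** Inputs: 383 girls; historical SAE rate 19/3,420 = 0.56%; vaccine-related SAE rate 2/3,420 = 0.058%.

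- At least one SAE: 1 − (1 − 19/3,420)^383 = 88.2% (stated 88.2%).
- At least one vaccine-related SAE: 1 − (1 − 2/3,420)^383 = 20.1% (stated 20.1%).
- Zero-event one-sided 95% upper limit: 1 − 0.05^(1/383) = 0.78%, or 1 in 128 (as stated).

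These figures are correct for all 383 girls. None of them is specific to the extension.

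**Size of the effect on the literal reading.** Let x be the number of girls with an extension SAE and f the share of the 383 who enter. The literal APaT proportion is x/383. The proportion among entrants is x/(383f). Their ratio is f, so the relative understatement is 1 − f.

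The documents do not give f, so it is an assumption. The table takes x = 5 for illustration, for which the literal result is 5/383 = 1.31% throughout.

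| f | entrants n | 5/n | relative understatement | zero-event limit, 1 − 0.05^(1/n) |
|---|---|---|---|---|
| 1.00 | 383 | 1.31% | 0 | 0.78% |
| 0.95 | 364 | 1.37% | 5% | 0.82% |
| 0.90 | 345 | 1.45% | 10% | 0.86% |
| 0.80 | 306 | 1.63% | 20% | 0.97% |
| 0.70 | 268 | 1.87% | 30% | 1.11% |
| 0.50 | 192 | 2.60% | 50% | 1.55% |

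The only related figure in the plan is the 10% attrition through Month 7 in Section 10.9.1. It covers both age groups and serves the immunogenicity sample size, so it is only a proxy for non-entry. It gives 383 × 0.90 = 344.7, about 345 entrants. At the historical rate, 345 × 0.00556 = 1.92 girls would have an SAE, and 1.92/383 = 0.50% against 0.56%. Each further 10 eligible girls who decline lower f by 10/383 = 0.026. That rate comes from earlier studies in girls aged 9-17 and is used here for scale only.

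**Which reading the text supports.**

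- Section 2 labels the extension columns with the 9-19 age range, so in that table the age label means the girls in the extension.
- Section 10.6.2 puts its sentence under an extension-stage heading and limits it to events during that stage.
- Section 10.1 can be read as the age group as it exists in the extension.
- Section 5.1 gives follow-up to Month 60 only to those who continue.
- Safety follow-up is itself a condition of APaT and is scheduled at all five extension visits. If it is applied to the period being summarized, girls who never entered drop out.

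On this reading numerator and denominator are the same girls and f = 1 (345/345 in the example).

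**The case for a change.** The best case for acting is that the plan often uses the phrase for the 9-19 group to mean the enrolled stratum. Section 6.1.2 uses it for base-stage enrolment, Section 6.2 for girls who are barred from the extension, and Section 10.9.2 for all 383. The wording of Section 10.1 therefore does not settle the matter alone. Extension results go into their own supplemental report, so the n printed there matters, and one sentence would fix it before the data are seen.

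Part of this stands: no sentence states the denominator, and entrants can only be a subset of the APaT girls. The contrast with immunogenicity is weaker than it looks. Section 10.6.1 names three-dose completers but not extension consent or entry, and Table 5 reuses the per-protocol population, whose criteria in Section 10.5.1 all concern Day 1 to Month 7. The plan carries base-stage population labels into the extension for both kinds of data and leaves it to the data available in that stage to narrow them. The risk of a choice made after seeing results is also slight, because there is no test or threshold to influence and the SAE count is the same under either denominator.

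**Conclusion.** The concern does not call for a change. The missing definition is real, but the downward bias exists only on a literal whole-study reading of APaT that the structure of the plan does not favour. Taking the denominator as girls followed in the extension is the ordinary choice for a stage-specific safety table, and the dilution factor is then 1.0.

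If the literal reading were used, the illustrative shift is from 0.56% to 0.50%, or 0.06 percentage points on about two girls with an SAE. This rests on the 10% proxy and would be larger if many eligible girls declined. H1, H2, the type I error, the power and the study's success criterion are untouched. No confidence interval or test is planned for this proportion. Section 10.6.2 reports counts with the proportion, so a reader who knows the number entering can recompute it. If the sponsor wishes to record the denominator, Section 10 already provides a supplemental SAP for non-confirmatory analyses before final database lock.

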10.6 Statistical Methods

10.6.1 Statistical Methods for Immunogenicity Analyses

Base stage:

V501 induced immune responses, as measured by cLIA anti-HPV 6, 11, 16 and 18 GMTs at 1 month post dose 3, will be analyzed separately. The statistical criterion for non-inferiority requires that the lower bound of two-sided 95% confidence interval of GMT ratio (girls vs. young women) being greater than 0.67 for each HPV type. The study will be considered a success for immunobridging if the non-inferiority criteria for GMTs are met for all 4 HPV types for the comparisons between girls aged 9-19 years vs. young women aged 20-26 years. Success on the seroconversion endpoints will provide further supporting evidence but is not required to declare study success. Anti-HPV 6, 11, 16, and 18 GMTs and seroconversion percentages measured by IgG LIA will be summarized as secondary objective of immunogenicity.

Immunobridging analysis

The primary hypotheses (H1) of non-inferiority of GMTs for each of HPV types 6, 11, 16 and 18 will be addressed by 4 one-sided tests of non-inferiority (one corresponding to each HPV type) conducted at the $\alpha=0.025$ level (1-sided). For each HPV type, the hypotheses to be tested are

$$H_0: \text{GMT}_1/\text{GMT}_2 \leq 0.67$$

$$H_a: \text{GMT}_1/\text{GMT}_2 > 0.67$$

where GMT_1 and GMT_2 represent the GMTs at 1 month post dose 3, in the 9-19 years old group and in the 20-26 years old group, respectively. The point estimate of GMTs will be calculated by taking the anti-natural-logarithm of the arithmetic mean of the natural-

logarithm-transformed anti-HPV titers. The test above will be conducted using an ANOVA model with a response of log individual titers and a fixed effect for comparison group. The statistical criterion for non-inferiority requires that the lower bound of two-sided 95% confidence interval of GMT ratio (9-19 years old vs. 20-26 years old) being greater than 0.67.

The secondary hypothesis (H2) of non-inferiority of seroconversion percentages for each of the vaccine HPV types (6, 11, 16 and 18) will be addressed by 4 one-sided tests of non-inferiority (one corresponding to each HPV type) conducted at the $\alpha=0.025$ level (1-sided).

The point estimate of seroconversion percentage for a particular HPV type is the ratio of the number of PPI-eligible participants for that particular HPV type who seroconverted to the relevant HPV type over the total number PPI-eligible participants for that particular HPV type who had evaluable Month 7 serology result based on serum sample collected within 31 to 49 days post dose 3.

For each HPV type, the hypotheses to be tested are

$$H_0: p_1 - p_2 \leq -0.05$$

$$H_a: p_1 - p_2 > -0.05$$

where p_1 is the proportion of participants who seroconvert by 1 month post dose 3 in the 9-19 years old group and p_2 is the proportion of participants who seroconvert by 1 month post dose 3 in the 20-26 years old group.

The tests above will be conducted using the method of Miettinen and Nurminen [Miettinen, O. and Nurminen, M. 1985]. The statistical criterion for non-inferiority requires that the lower bound of two-sided 95% confidence interval for the difference (9-19 years old minus 20-26 years old) in seroconversion percentages being greater than -5 percentage points for each HPV type.

Table 4 summarizes the immunogenicity analyses for the base stage.

Table 4 Analysis Strategy for Immunogenicity Variables— Base Stage

Endpoint/Variable (Description, Time Point)	Primary vs. Supportive Approach [†]	Statistical Method	Analysis Population	Missing Data Approach
Primary Objective				
Anti-HPV 6, 11, 16 and 18 cLIA GMTs at Month 7 (each type will be tested separately)	P	Point and 95% CI estimation as well as statistical testing will be performed by using an ANOVA model.	PPI	Observed data only
Anti-HPV 6, 11, 16 and 18 cLIA GMTs at Day 1 and Month 7	S	Point and 95% CI estimation will be provided by using an ANOVA model.	ANPS	Observed data only

Endpoint/Variable (Description, Time Point)	Primary vs. Supportive Approach [†]	Statistical Method	Analysis Population	Missing Data Approach
Secondary Objective				
cLIA % seroconversion to HPV 6, 11, 16, 18 by Month 7 (each type will be tested separately).	P	Point and 95% CI estimation as well as statistical testing of binomial proportion based on Miettinen & Nurminen method	PPI	Observed data only
Anti-HPV 6, 11, 16 and 18 IgG LIA GMTs at Day 1 and Month 7	S	Point and 95% CI estimation will be performed by using an ANOVA model.	PPI	Observed data only
IgG LIA % seroconversion to HPV 6, 11, 16, 18 by Month 7	S	Point and 95% CI estimation based on exact method	PPI	Observed data only

[†] P=Primary approach; S=Supportive approach.

[‡] Statistical models are described in further detail below:

ANPS = all type-specific naïve participants with serology; CI = confidence interval; GMT = geometric mean titer; PPI = per-protocol immunogenicity.

PBNA results (GMTs and seroconversion percentages) will be summarized as exploratory objective. The PBNA results of the base stage may be summarized in a supplemental report after the data are available.

Extension stage:

Participants in the 9-19 years old group who have completed 3 doses of study vaccination will be followed up to Month 60 to evaluate the persistence of the serum antibody titers for each of HPV 6, 11, 16 and 18 at Month 12, Month 24, Month 36, Month 48, and Month 60. Both cLIA and IgG LIA will be used to measure GMTs and seropositivity percentages.

Table 5 summarizes the immunogenicity persistence analyses for the extension stage.

Table 5 Analysis Strategy for Immunogenicity Variables – Extension Stage

Endpoint/Variable (Description, Time Point)	Primary vs. Supportive Approach [†]	Statistical Method	Analysis Population	Missing Data Approach
cLIA GMTs to HPV 6, 11, 16 and 18 at Month 12, Month 24, Month 36, Month 48, and Month 60	P	Point and 95% CI estimation will be performed by using an ANOVA model; no statistical testing and between group 95% CI will be given.	PPI	Observed data only
cLIA % seropositivity to HPV 6, 11, 16 and 18 at Month 12, Month 24, Month 36, Month 48, and Month 60	P	Point and 95% CI estimation based on exact method; no statistical testing and between group 95% CI will be given.	PPI	Observed data only
IgG LIA GMTs to HPV 6, 11, 16 and 18 at Month 12, Month 24, Month 36, Month 48, and Month 60	P	Point and 95% CI estimation will be performed by using an ANOVA model; no statistical testing and between group 95% CI will be given.	PPI	Observed data only
IgG LIA % seropositivity to HPV 6, 11, 16 and 18 at Month 12, Month 24, Month 36, Month 48, and Month 60	P	Point and 95% CI estimation based on exact method; no statistical testing and between group 95% CI will be given.	PPI	Observed data only
cLIA GMTs to HPV 6, 11, 16 and 18 at Month 12, Month 24, Month 36, Month 48, and Month 60	S	Reverse cumulative distribution curve (RCD) at Month 12, Month 24, Month 36, Month 48, and Month 60	PPI	Observed data only

[†] P=Primary approach; S=Supportive approach.
CI = confidence interval; GMT = geometric mean titer; PPI = per-protocol immunogenicity.

PBNA results (GMTs and seropositivity percentages) will be summarized as exploratory objective. The results of PBNA may be summarized in a supplemental report upon its availability.

